5.7 Blinding

The trial products (i.e. Acipimox, Salbutamol, or placebo) will be received by the Clinical Trials Pharmacy in a distinguishable manner. They will be handled only by unblinded personnel until repackaged in an opaque container. Each container will be labelled with a unique pack ID to identify each pack and its content. The treatment will be prescribed by [name], and dispensed to the participant by the Pharmacy. Participants will be instructed not to discuss the product they receive with anyone inside or outside the research team.

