11.1 Research Ethics Committee (REC) review and reports	
11.2 Peer review	
11.3 Indemnity	
12. DISSEMINATION POLICY	30
13. REFERENCES	31

ii. LIST OF ABBREVIATIONS

BCAA	Branched-chain amino acid
BCKDH	Branched-chain alpha-keto acid dehydrogenase
CI	Chief Investigator
CRF	Case Report Form
CSA	Cross-sectional area
CTIMP	Clinical Trial of Investigational Medicinal Product
GCP	Good Clinical Practice
GLP	Good laboratory practice
MHRA	Medicines and Healthcare products Regulatory Agency
PDC	Pyruvate dehydrogenase complex
PI	Principal Investigator
REC	Research Ethics Committee
SAE	Serious Adverse Event
SOP	Standard Operating Procedure
TMF	Trial Master File

iii. TRIAL SUMMARY

Trial Title	The impact of Acipimox and Salbutamol supplementation on the development of insulin resistance and anabolic resistance during forearm immobilization in healthy, young volunteers	
Short title	Forearm immobilization, metabolic health, and muscle loss	
Trial Design	Randomized, double-blind, placebo-controlled trial with three parallel groups	
Study category	Basic science study involving procedures with human participants	
Trial Participants	Young healthy recreationally active males and females	
Planned Sample Size	45	
Treatment duration	2 days of forearm immobilization plus drug or placebo ingestion	
Planned Trial Period	Minimally 12 days (screening, baseline metabolic test day, approximate 7 days waiting period, 2 days forearm immobilization), maximally 33 days (waiting period can be up to 4 weeks, depending on availability of the participant).	
Study sites	
Royal Devon & Exeter NHS Foundation Trust Clinical Research Facility (CRF) and Clinical Trials Pharmacy Activities: screening and consenting (CRF), forearm cast application and removal (CRF), metabolic testing (CRF), drug dispensing to study participants (Pharmacy)
 
Nutritional Physiology research laboratories St Luke's Campus, University of Exeter Activities: preparation of a standardised diet, plasma analyses. If required: screening and consenting, forearm cast application
	
	Objectives	Outcome Measures
Primary	Determine the impact of reduced muscle lipid availability and increased glycolytic flux on forearm glucose uptake during short-term forearm immobilization in healthy volunteers	Forearm glucose uptake

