- At t = 2.5 h, a hyperinsulinaemic-euglycaemic-hyperaminoacidaemic clamp will be started. For this, insulin will be infused at a rate of 50 mU·m⁻²·min⁻¹, and a simultaneous infusion of 20% glucose will be started to maintain euglycaemia at 5.0 mmol·L⁻¹. A 0.3% potassium chloride solution will be infused in the (to be) immobilized arm at a rate of 1 ml/kg body weight/h during the 3-h clamp to maintain plasma potassium concentrations [25]. Hyperaminoacidaemia will be induced by infusion of an amino acid solution (Primene 10%, Baxter) at BCAA concentrations of 700 μmol·L⁻¹. This concentration was chosen as it is the average postprandial BCAA concentration following mixed meal ingestion in the pilot study. Primene will be 7% enriched with L-[ring-²H₅]-phenylalanine to prevent a decrease in plasma enrichments with Primene infusion. Measurements of blood glucose (Yellow Springs Instruments; every 5 min) and BCAA (spectrophotometric assay, [26]; every 20 min) concentrations will be performed at the bedside, and the infusion rate of glucose and amino acids adjusted accordingly to maintain steady state. Throughout the entire 5.5 h infusion period, repeated arterialised-venous (AV) and deep-venous (V) blood samples will be taken in order to calculate forearm AV-V balance of glucose (i.e. insulin sensitivity), amino acids, and free fatty acids using the Fick principle [27]. Prior to every blood sample, brachial artery blood flow will be measured using Doppler ultrasound.

- After 2 hours of the 3h clamp, a single dose of 10 mg metoclopramide hydrochloride will be administered intravenously in an antecubital elbow cannula, to prevent potential gastrointestinal issues during the final hour of the clamp.
- Following the 3 h clamp, infusion of insulin, amino acids and stable isotope amino acids will be stopped while infusion of glucose will be decreased in a stepwise manner based on blood glucose concentrations. The last 30 min of the clamp will be used to calculate the mean glucose infusion rate (GIR) and mean amino acid infusion rate. Participants will be monitored for minimally 20 min following cessation of the glucose infusion before they are allowed to leave the laboratory.

Forearm casting and drug dispensing (visit 3; to take place between 7 and 28 days after visit 2):

- In the morning at 7:30 AM, participants will visit the Clinical Research Facility at the Royal Devon & Exeter NHS Foundation Trust in an overnight fasted state.

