5.6 Randomisation

To determine whether altering muscle substrate availability impacts upon metabolic health, participants will be asked to take an oral supplement 4 times a day during the 2-day forearm immobilization period. Participants will be randomly allocated to receive a supplement containing either acipimox, salbutamol, or a placebo containing only cellulose microcrystalline.

Randomisation will be via a computer generated randomisation schedule provided by the involved statistician ([name]), and held in a folder in his office in Richards Building (St Luke's Campus). A secure Excel document of the randomization schedule (treatment A, B, or C) will be accessible by all members of the study team, including [name] and the Pharmacy contact. Supplementation compliance will be monitored via self-reported supplement intake diaries, and content counting from returned supplement containers.

The arm-to-be-immobilized will be counterbalanced between the dominant and non-dominant arm.

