7 TRIAL TREATMENTS

The present study is a basic physiology study, which aims to elucidate mechanisms underlying muscle atrophy by studying muscle metabolism in conditions of pharmacologically altered substrate availability. Participants will be randomized to receive one of two drugs (Acipimox and Salbutamol) or a placebo, to be taken orally during the 2-day forearm immobilization period. Products will be prescribed by [name], after thorough checking for the listed in- and exclusion criteria (Section 6).

All products will be taken 4 times daily, with or after the three main meals (i.e. breakfast, lunch, dinner), and before bed.

Participants will be able to contact the CI 24/7, and [name] will be available for advice throughout the supplementation period.

The study products are described below:

Acipimox

The drug Acipimox is a nicotinic acid analogue that inhibits adipose tissue lipolysis, lowers intramuscular lipid metabolites, and improves insulin sensitivity. Acipimox will be given in 250 mg capsules, taken 4 times daily, as this dose has been shown to improve insulin sensitivity in type 2 diabetes patients within a few days [20].

Acipimox may cause some mild-moderate side effects in approximately 2 out-of 10 people. These side effects can include: skin rash; red 'flushed' skin; itching; sensations of hot skin. Less common effects include stomach pain and weakness.

Salbutamol

The drug Salbutamol is a β 2-adrenoceptor agonist commonly used as a bronchodilator in asthma. In addition, β 2-agonists have been shown to stimulate glycogenolysis and glycolytic flux [21], and exert a hypertrophic effect [22] by increasing muscle protein synthesis and decreasing proteolysis [23, 24]. Salbutamol will be given in 4 mg tablets, taken 4 times daily, as this dose has been shown to lead to a significant increase in lean mass in [22].

Salbutamol may cause mild-moderate side effects in approximately 1 out-of 10 people. These side effects can include fine tremor ('shaking', especially of the hands), headache, dizziness, and nausea. Less common side effects include arrhythmias, low blood pressure, and muscle pain.

Placebo

The placebo supplement will contain lactose, microcrystalline cellulose, pregelatinised starch, sodium starch glycolate, and magnesium stearate. These are inert substances widely used in many pill and tablet formulations, and are unlikely to cause toxicity when taken orally.

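### The masking described (an opaque pack) does not make a capsule, a tablet and a single placebo look alike, so the double-blind label is not assured

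*Combined protocol and SAP*

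**What the plan says.** The Trial Summary describes the study as "Randomized, double-blind, placebo-controlled trial with three parallel groups". The statements that bear on whether the products can be told apart are these:

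- **Dosage forms (section 7).** "Acipimox will be given in 250 mg capsules, taken 4 times daily"; "Salbutamol will be given in 4 mg tablets, taken 4 times daily".
- **Placebo.** Section 7 lists five ingredients: "The placebo supplement will contain lactose, microcrystalline cellulose, pregelatinised starch, sodium starch glycolate, and magnesium stearate". Section 5.6 describes "a placebo containing only cellulose microcrystalline". Neither section says whether it is a capsule or a tablet.
- **Masking (section 5.7).** The products reach the pharmacy in distinguishable form. "They will be handled only by unblinded personnel until repackaged in an opaque container". Each container carries a pack ID. Participants are told not to talk about their product with anybody, study staff included.
- **Compliance (section 5.6).** "Supplementation compliance will be monitored via self-reported supplement intake diaries, and content counting from returned supplement containers". The person who counts is not named.
- **Schedule (section 5.6).** The list of A, B or C allocations is open to the whole study team.
- **Primary outcome (section 5.5).** Forearm glucose uptake is calculated by the Fick principle. "Prior to every blood sample, brachial artery blood flow will be measured using Doppler ultrasound".

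No section mentions over-encapsulation, matched appearance or a double dummy. None says who performs or reads the Doppler scans, or whether that person is kept away from returned product.

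**The concern.** A participant opens the pack for each of eight doses, so blinding depends on what the units look like, and the plan says nothing to make them alike. If staff then learn the form, through the return count, the first dose at visit 3 or a participant's remark, the open A/B/C list can extend one recognition to everyone under the same letter.

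The exposed measurement is brachial flow, the operator-dependent factor in the primary outcome. It also enters the amino acid and fatty acid balances. Baseline (visit 2) precedes treatment, so any bias from knowing the arm would fall on visit 4 alone. It would pass straight into the treatment-by-time contrast that section 9.3.2 tests.

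**Working it through.** **1. Can one placebo match both drugs?** The forms come from section 7. The placebo form is unstated, so take each case.

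| Placebo form | Acipimox (capsule) vs placebo | Salbutamol (tablet) vs placebo |
|---|---|---|
| Capsule | same form | differs |
| Tablet | differs | same form |
| Other | differs | differs |

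Every row has at least one mismatch. A shared form does not guarantee the same size or colour either. The opaque container does not change this. It is the pack and not the dose unit, since it carries a pack ID and its contents are later counted.

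**2. Routes from product to measurer.**

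- Return count: the counter is unnamed, and nothing separates this person from the visit 4 scans.
- First dose: taken at visit 3; who is present is not stated.
- Disclosure: restrained only by the instruction in section 5.7.
- Spread: the team-wide A/B/C list.

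Each route is open on the text. None is documented as happening.

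**3. The plan's own figures (section 9.1).** Two-sample t-test, two-sided alpha 0.05, power 80%:

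- Acipimox: d = 13/8 = 1.625. n = 8 per group gives power 0.856 (n = 7 gives 0.797).
- Salbutamol: d = (13 − 4.3)/√((8² + 6²)/2) = 8.7/7.07 = 1.23. n = 12 gives power 0.821 (n = 11 gives 0.783).
- Dropout: 12/0.8 = 15 per group; 3 × 15 = 45.

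The stated sample size reproduces, and this point does not alter it.

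**4. Sensitivity of the outcome to a diameter reading.** Assume flow = mean velocity × vessel area, with velocity and the AV-V difference fixed. Uptake then scales with diameter squared. The protocol does not describe how diameter is read.

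- Salbutamol (−4.3%) vs placebo (−13%): 0.957/0.87 = 1.100; √1.100 = 1.049, a 4.9% diameter shift.
- Acipimox (0%) vs placebo (−13%): 1/0.87 = 1.149; √1.149 = 1.072, a 7.2% shift.

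The percentages do not depend on artery size. On an assumed 4 mm artery they are 0.20 mm and 0.29 mm; over 3 to 5 mm they are 0.15 to 0.24 mm and 0.22 to 0.36 mm.

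**5. What a smaller bias would do.** Assume no true effect, 12 per group, an unadjusted two-sided 5% t-test on the change, and one arm's measured change shifted by b percentage points.

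| b | False-positive rate, SD 8 | False-positive rate, SD 7.07 |
|---|---|---|
| 1 | 6% | 6% |
| 2 | 9% | 10% |
| 3 | 14% | 17% |
| 4 | 22% | 26% |
| 6 | 42% | 51% |

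The smallest observed difference that reaches p < 0.05 is about 6.8 points (SD 8) or 6.0 points (SD 7.07). On the scale of step 4, a 3-point shift is √(0.90/0.87) = 1.017, or 1.7% in diameter. The values of b are assumptions, because the documents give none. The planned Bonferroni adjustment would lower these rates.

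**The case against.** The strongest reply is that this reads silence as fact. Section 5.7 confines handling to unblinded staff until repackaging, which suggests that repackaging is meant to end the distinguishability. A pharmacy procedure outside the protocol may make the units identical. Wording on form is loose elsewhere: the exclusion criteria in section 6.2 refer to tablets for the products generally. What stands is that the intention is visible and such a procedure may exist. It does not remove the gap, because the step described is an opaque pack and the forms in section 7 differ.

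A second reply is that different is not the same as recognised. Each participant sees one product and cannot compare it, and nothing available says participants are told which drug has which form. With eight doses and no stated surplus, a compliant participant may return an empty container. Section 5.6 does not say whether the count comes before the visit 4 scans. This stands, and it limits the claim to blinding that is not assured.

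A reader might go further in three ways that the documents do not support:

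- **That the trial is unblinded, or that the Doppler operator knows the arm.** This needs a second step, such as counting before measurement or disclosure despite the instruction, and none is documented. Masked Doppler reading is not excluded either.
- **That hand adjustment of the clamp, or the participant's own knowledge, biases uptake.** Glucose is read by an analyser every 5 minutes and titrated to a fixed 5.0 mmol/L, and infusion rate is not the primary outcome. No mechanism is given by which a participant's belief would change forearm uptake under the clamp.
- **That the 4.9% and 7.2% shifts estimate the bias.** They would have to be systematic, confined to one arm and to visit 4, and persist over repeated readings. Nothing indicates that this would happen.

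Finally, tremor with Salbutamol and flushing with Acipimox (sections 3 and 7) may unmask some participants whatever the units look like. That is true, but it does not justify leaving an avoidable cue present at every dose.

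**Conclusion.** The point holds as a mismatch between the label and the procedure. Followed as written, the plan leaves at least one active arm different in form from placebo, and the placebo itself is described in two ways that must be reconciled before anything can be matched to it. The unassigned return count and the team-wide A/B/C list give that difference possible routes to the staff who measure flow. The instruction in section 5.7 is a partial safeguard.

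The size of any bias is unknown. The diameter and false-positive figures show only that the primary contrast is sensitive to modest differential error. They rest on flow scaling with diameter squared, on the plan's own means and SDs, and on assumed shifts. The conclusion also assumes that no procedure outside the protocol makes the units identical; if one exists, stating it would settle the appearance part of the point. It should be settled before dosing starts, because blinding cannot be restored for participants already treated.

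**What to change.** 1. **Sections 5.7 and 7.** State the form and appearance of all three products and how they are made identical, for example by pharmacy over-encapsulation in the same opaque capsule with doses unchanged. Give one placebo composition, reconciled between sections 5.6 and 7.
2. **Section 5.6, returns.** Have the unblinded pharmacy receive and count returned containers, and keep the contents away from staff who scan or analyse.
3. **Section 5.6, schedule.** Restrict the A/B/C list to the statistician and the pharmacy, keeping the emergency unblinding route in section 8.3.
4. **Section 5.5.** Store Doppler clips under a code and have existing staff read them off-line, masked to participant and visit, preferably someone other than the person who scanned.

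The cost is capsule shells and pharmacy time for up to 45 × 8 = 360 dosing occasions, some reading time, and protocol wording. The capsule may be larger to swallow. The sample size does not change. Off-line reading does not mask acquisition of the images, and side effects will still hint at allocation in some participants, so the fix reduces the risk without removing it.

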5.8 Storage and analysis of clinical samples

Blood samples will be taken throughout the study, as outlined in the study protocol. At each sampling point 8 mL of blood will be taken via cannula, and immediately divided into a plasma (BD Vacutainer - lithium heparin) and serum tube (BD Vacutainer – SST). Plasma samples will be directly snap frozen in liquid nitrogen and analysed for branched-chain amino acids and non-esterified fatty acid concentrations. Serum will be allowed to clot for 30 minutes prior to centrifugation, before being aliquoted into Eppendorf's, snap frozen in liquid nitrogen, and stored in a freezer at $-80^{\circ}\text{C} \pm 10^{\circ}\text{C}$ until analysis for insulin concentration. Plasma L-[*ring*- $^2\text{H}_5$]-phenylalanine enrichments will be measured via gas chromatography-mass spectrometry (GC-MS; [6]). The CI will keep a record of all blood samples taken, of their respective aliquots, and of their location within the freezer.

Samples will be stored for a period of 5 years, in line with HTA guidelines, for further analysis beyond the primary variables depending on the changing landscape of the literature. Samples will be stored in a secure location accessible only via security-card access. Samples will be destroyed either in the process of analysis, or, after the allotted storage period has passed, by being placed in clinical waste and subsequently incinerated. Disposal of plasma and serum will be recorded by the research team in their own archives. Overall responsibility for the samples will reside with [name]. Samples will be appropriately labelled in accordance with the trial procedures to comply with the 1998 Data Protection Act. Biological samples collected from participants as part of this trial will be transported, stored, accessed and processed in accordance with national legislation relating to the use and storage of human tissue for research purposes and such activities shall at least meet the requirements as set out in the 2004 Human Tissue Act and the 2006 Human Tissue (Scotland) Act.

6 PARTICIPANT ELIGIBILITY CRITERIA

6.1 Inclusion criteria

- Males and females 18-40 years of age
- Body mass index between 18.5 and 30 kg/m²

6.2 Exclusion criteria

- Any diagnosed metabolic impairment (e.g. type 1 or 2 diabetes)
- Any diagnosed cardiovascular disease
- Hypertension (≥ 140 mmHg systolic and/or ≥ 90 mmHg diastolic)
- Chronic use of any prescribed or over the counter pharmaceuticals (excluding oral contraceptives and contraceptive devices)
- Regular use of nutritional supplements
- A personal or family history of thrombosis, epilepsy, seizures or schizophrenia
- Any previous motor disorders
- Any known disorders in lipid metabolism
- Any known disorders in muscle metabolism
- Known allergy for Acipimox, Salbutamol, or other substances in the tablets
- Known sensitivity for sympathomimetic drugs
- Known hypokalaemia
- Presence of an ulcer in the stomach or gut and/or strong history of indigestion
- Known severe kidney problems
- Previous reaction to metoclopramide
- Known pheochromocytoma (tumour that secretes noradrenaline or adrenaline) or past history of one
- Recent abdominal surgery
- Pregnancy
- Unable to give consent

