5.2 Screening

Participants will be asked to meet the investigator so that the study can be explained to them in detail, and it is clear what they can expect from the research team and what will be expected of them. Assuming they are happy with what has been discussed, they will then provide written consent. Subsequently, they will complete a medical screening questionnaire and have their height, weight, body composition, and blood pressure measured. All in-and exclusion criteria (please see Section 6) will be assessed. The CI will discuss any issues about eligibility to take part with the medical collaborator.

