5.5 Trial procedures

Please refer to page 11 for trial flow chart and schematic of the metabolic test days. The trial procedures are described below:

Screening visit (visit 1):

- Firstly, participants will be asked to meet the investigator so that the study can be explained to them in detail, and it is clear what they can expect from the research team and what will be expected of them. Assuming they are happy with what has been discussed, they will then provide written consent. Subsequently, they will complete a medical screening questionnaire and have their height, weight, body composition (Bodpod), and blood pressure measured.
- Participant's caloric requirements will be calculated by estimating Resting Metabolic Rate via the Henry equation, and then multiplying this value by an activity factor derived from the International Physical Activity Questionnaire (IPAQ) questionnaire.
- Forearm volume will be measured via anthropometry.
- Participants will be asked for any allergies or intolerances to ensure they can eat everything they will receive as part of the standardized diet.
- Participants will be provided with a food diary to record their habitual dietary intake for 3 consecutive days, including 2 week days and 1 weekend day.

Baseline metabolic test day (visit 2):

- Approximately 1 week prior to casting, at 8 AM, participants will visit the Clinical Research Facility at the Royal Devon & Exeter NHS Foundation Trust in an overnight fasted state for a metabolic test day.
- The following cannulas will be inserted by a trained research nurse: 1) retrogradely into a deep antecubital vein (draining the muscle bed) of the non-immobilised arm, 2) retrogradely into a superficial dorsal hand vein of the to-be-immobilised hand, and 3) anterogradely into an antecubital vein in the elbow of the to-be-immobilised arm for infusion of insulin, glucose, amino acids, and stable isotope amino acids. The cannulated hand will be placed into a hand-warming unit (air temperature 55°C) to arterialize the venous drainage of the hand.
- After insertion of all cannulas, a primed, continuous stable isotope infusion of L-[ring-²H₅]-phenylalanine (prime: 0.5 mg·kg⁻¹, infusion 0.5 mg·kg⁻¹·h⁻¹) will be started with participants in a supine position. Using this tracer approach we will be able to calculate muscle protein synthesis and plasma leucine oxidation.

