10.2 Data areas and data types

The research data to be managed are principally quantitative in nature obtained from investigation of healthy young male and female participants (18-40) e.g. screening data (height, weight, BMI, age, blood clinical chemistry, blood pressure, forearm volume etc.), habitual diet, body composition and muscle mass obtained from BodPod, and muscle protein synthesis rates and plasma tracer enrichments and/or amino acid and fatty acid concentrations of the collected blood samples. A proportion of the data will be qualitative (e.g. screening and physical activity questionnaires and diet diaries).

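### Pregnancy is an unqualified exclusion in a trial open to women aged 18-40, but no visit described in section 5 includes a pregnancy test before the clamps or the study drug

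*Combined protocol and SAP*

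**What the plan says.** Section 6.1 admits males and females aged 18-40. Section 6.2 ties several exclusions to what is already on record: "Known hypokalaemia" is one, severe kidney problems must likewise be known, and metabolic impairment must be diagnosed. Pregnancy appears with no such condition.

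On how eligibility is established, section 5.2 says of consenting volunteers that "they will complete a medical screening questionnaire and have their height, weight, body composition, and blood pressure measured". It adds "All in-and exclusion criteria (please see Section 6) will be assessed", without a method for each criterion. Section 5.5 repeats for visit 1 that participants "have their height, weight, body composition (Bodpod), and blood pressure measured", and adds an estimate of energy needs, forearm anthropometry, questions on allergies and a food diary. Neither section mentions a blood or urine sample at screening.

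Section 5.5 puts the first clamp at visit 2, casting and the first dose at visit 3 (7 to 28 days later), and the second clamp at visit 4, two days after visit 3. Section 7 has the prescriber go through the criteria before prescribing, but gives no date and names no test.

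Section 10.2 describes the data to be held as including "screening data (height, weight, BMI, age, blood clinical chemistry, blood pressure, forearm volume etc".

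**The concern.** Pregnancy is the one exclusion of this kind that does not depend on prior knowledge: a woman who is pregnant and unaware of it is ineligible under section 6.2. The only screening tool described that could bear on it is the questionnaire, and a questionnaire cannot find what the volunteer does not know. She would be admitted against the plan's own criterion and go through the clamp procedure twice, possibly with a study drug between. The plan treats this exposure as one to avoid: it excludes pregnancy, and section 8.1 lists a congenital anomaly in a participant's offspring among the serious adverse event outcomes.

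The secondary issue is one of documentation. Staff following section 5 would take no screening blood; staff reading section 10.2 would expect chemistry results. Neither says which analytes are meant or who reviews them.

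**Working it through.** The plan states no figure to reproduce here. The check sets the sections side by side.

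**1. Exclusions against the checks described**

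| Exclusion (6.2) | Qualifier | Matching check in section 5 |
|---|---|---|
| Hypertension | Numeric limits (140/90 mmHg) | Blood pressure measured at visit 1 |
| Hypokalaemia | Known | History is enough for the wording |
| Severe kidney problems | Known | History is enough for the wording |
| Metabolic impairment | Diagnosed | History is enough for the wording |
| Pregnancy | None | No test at visits 1, 2, 3 or 4 |

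Only the last row has a criterion that the described procedures cannot fully apply.

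**2. Timing (section 5.5).** Take visit 2 as day 0.
- Visit 3 (first dose): day 7 to day 28.
- Visit 4 (second clamp): two days later, day 7 + 2 = 9 to day 28 + 2 = 30.

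A negative test at visit 2 would be 7 to 28 days old at the first dose and 9 to 30 days old at the second clamp. A test at visit 3 would be two days old at the second clamp. Two tests therefore cover all the exposures, and one at visit 2 does not.

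**3. Exposure of an undetected case.** Clamps: 2 × 3 h = 6 h. Doses: 4 per day × 2 days = 8. With 15 per group, 30 of the 45 recruited are allocated an active drug.

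**4. Number of tests.** The split by sex is not given. If F of the 45 recruited are women, at most 2F dipsticks are needed: from 0 (F = 0) to 90 (F = 45).

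**5. Room for late exclusions (section 9.1).** Recruitment of 45 against 3 × 12 = 36 completers leaves 9 places, or 3 per group. A few exclusions at visit 2 or 3 fit within this if other dropout leaves space.

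**6. Screening chemistry.** Section 3 places all six cannulas on the two metabolic test days. Section 5.8 says samples are drawn through a cannula, and names assays for branched-chain amino acids, fatty acids, insulin and tracer enrichment. None of this points to a screening sample, and no potassium, creatinine or pregnancy assay is named. Section 10.2 says otherwise about chemistry. The text is inconsistent; it does not show which version is right.

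**The case against.** A reader might infer something stronger: that the potassium, kidney and metabolic exclusions also fail for want of a laboratory test, and that all 45 participants receive potassium with no baseline value on file. The documents do not support this, for four reasons.

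- Those three criteria are limited to known or diagnosed conditions, so asking the volunteer applies them exactly as written. Widening them would be a new eligibility rule.
- Because section 10.2 lists screening chemistry, the absence of a potassium or creatinine value is not established.
- The potassium infusion is there "to maintain plasma potassium concentrations". Its dose is 3 mg/ml × 1 ml/kg/h × 3 h = 9 mg/kg, which at an assumed 70 kg is 630 mg, or 630 / 74.55 = 8.45 mmol. That is a dose, not a measure of harm.
- The plan has other safeguards: chronic medication is excluded (contraceptives apart), medical cover is in the building during insulin infusion, and glucose is measured every 5 minutes during the clamp.

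On pregnancy itself, the best defence is that section 5.2 promises assessment of every criterion, that the questionnaire and flow chart are not available to read, and that section 7 adds a check before prescribing. Part of this stands. A test shown only in the flow chart cannot be ruled out. Since the prescriber's check is undated, the age of the pregnancy answer at first dose is also unknown: the 7 to 28 days is the gap between visits, not an established age of the answer. But none of these places names a test in the text, and the section 7 check is tied to prescribing the products, while the first clamp comes earlier, at visit 2. The general safeguards above do not detect pregnancy.

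**Conclusion.** The point holds for pregnancy. As written, an unqualified exclusion rests on self-report before two clamps and possible acipimox or salbutamol dosing. The gap applies to every woman enrolled; any harm would fall only on those with an unrecognised pregnancy. Their expected number cannot be calculated, because the plan gives neither the number of women nor a pregnancy rate. The conclusion assumes that the written procedures in section 5 are what staff will follow, and that the flow chart adds no test.

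The mismatch between section 10.2 and sections 5.2 and 5.5 is real but secondary, and calls for a correction to the text. The potassium, kidney and metabolic exclusions can be applied by history as they stand. Nothing here affects the sample size calculation or the analysis.

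**What to change.** Add to section 5.5 a urine pregnancy test for women on arrival at visit 2, before the clamp, and at visit 3, before dispensing. State that a positive result excludes the participant. Both visits already take place, so the cost is two dipsticks per woman and possibly a few late exclusions, including some women who have already completed the first clamp.

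Reconcile section 10.2 with sections 5.2 and 5.5. If screening chemistry is taken, write it into visit 1, name potassium and creatinine among the analytes, and have the medical collaborator review the results before visit 2. If it is not taken, delete it from section 10.2.

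Rewording the known or diagnosed exclusions, or adding a fasting glucose, is optional. It costs more than a text change: only visits 2 to 4 are described as fasted, so a fasting glucose would need a fasted visit 1. At the 50% screening failure allowed in section 9.2, up to 45 / 0.5 = 90 volunteers would be sampled.
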